7.2 Hypoglycemia and Hyperglycemia Prevention and Treatment

Table 8. Hypoglycemia and Hyperglycemia Prevention and Treatment

Condition	Action Taken – Inpatient Study	Action Taken – Outpatient Extension
HMS alert for impending hypoglycemia	Study staff will closely monitor the subject's CGM readings for potential hypoglycemia during the 48-hour session. A confirmatory fingerstick measurement will be performed. If fingerstick glucose \geq 63 mg/dL, treatment may be initiated by the investigator (~4-16 g fast acting carbohydrate) per investigator discretion. Subjects will then perform a follow-up fingerstick measurement 15 minutes after	Subject is instructed to perform a confirmatory fingerstick measurement for all predictive low alarms. If fingerstick glucose \geq 63 mg/dL, treatment may be initiated with ~4-16 g fast acting carbohydrate. Subjects will then perform a follow-up fingerstick measurement 15 minutes after treatment if CGM < 63 mg/dL. This protocol will be repeated until the HMS alert stops alarming. If fingerstick glucose < 63 mg/dL, treatment will be initiated with ~4-16

	
treatment if CGM < 63 mg/dL. This protocol will be repeated until the HMS alert stops alarming.
 
If fingerstick glucose < 63 mg/dL, treatment will be initiated by the investigator (~4-16 g fast acting carbohydrate) per investigator discretion. Subjects will then perform a follow-up fingerstick measurement 15 minutes after treatment if CGM < 63 mg/dL. This protocol will be repeated until the HMS alert stops alarming.
	
g fast acting carbohydrate). Subjects will then perform a follow-up fingerstick measurement 15 minutes after treatment if CGM < 63 mg/dL. This protocol will be repeated until the HMS alert stops alarming.

CGM reading <63 mg/dL	
Same as above treatment. This protocol will be repeated until the fingerstick is >63 mg/dL per standard clinical treatment for hypoglycemia.
	
Same as above treatment. This protocol will be repeated until the fingerstick is >63 mg/dL per standard clinical treatment for hypoglycemia.
 
During the first two weeks of outpatient use, study investigators will receive alerts for prolonged states of hypoglycemia.

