Any time a subject has subjective symptoms of hypoglycemia	
A fingerstick blood glucose measurement will be performed. Fast-acting carbohydrates may be given to any subject who is symptomatic or requests treatment.
	
Subject is instructed to perform a fingerstick blood glucose measurement for symptoms of hypoglycemia. Fast-acting carbohydrates may be taken at any time for hypoglycemia symptoms.

CGM reading is >180 mg/dL for more than 1 hour	
A confirmatory fingerstick measurement will be performed.
 
If the subject's BG is confirmed to be >180 mg/dL, then ketones will be checked using the study-approved ketone meter.
	
Subject is instructed to perform a fingerstick blood glucose measurement.
 
If the subject's BG is confirmed to be >180 mg/dL, then ketones will be checked using the study-approved ketone meter.
 
Study investigators will receive alerts for prolonged states of hyperglycemia.

BG confirmed >180 mg/dL for more than 1 hour and	
A manual correction bolus with a target of 140 mg/dL may be delivered via the pump. Fingerstick BG and ketone measurements will be repeated after 1 hour. The correction
	
Subject will deliver a manual correction bolus with a target of 140 mg/dL via the pump. Fingerstick BG and ketone measurements will be repeated after 1 hour. The correction

ketones are <1.0 mmol/L
	
dose given may be adjusted by the investigator, or by the subject during extended use of the system at home.
 
If BG fails to decrease by a minimum of 50 mg/dL in 1-2 hours, then study staff will replace the subject's infusion set with a new infusion set and the correction bolus will be repeated per the investigator's discretion. Subjects will change out their own infusion set during extended use of the system at home.
	
dose given may be adjusted by the subject during extended use of the system at home.
 
If BG fails to decrease by a minimum of 50 mg/dL in 1-2 hours, then subject will replace their infusion set with a new infusion set and the correction bolus will be repeated as needed.
 
During the first two weeks of outpatient use, study investigators will receive alerts for prolonged states of hyperglycemia.

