
BG confirmed >180 mg/dL for more than 1 hour and ketones are >1.0 mmol/L
	
A manual correction bolus with a target of 140 mg/dL may be delivered via injection to assure proper absorption in the setting of likely infusion set failure. Fingerstick BG and ketone measurements will be repeated after 1 hour. The correction dose given may be adjusted by the investigator, or by the subject during extended use of the system at home.
 
The study staff will replace the subject's infusion set with a new infusion set and the correction bolus will be repeated per the investigator's discretion. Closed-loop will be disabled by the investigator for the next 2-4 hours and until BG has returned to < 180 mg/dL. Subjects will change out their own infusion set and stop closed-loop use during extended use of the system at home.
	
Subject is instructed that with positive ketones, a manual correction bolus with a target of 140 mg/dL is to be given via injection to assure proper absorption in the setting of likely infusion set failure. Fingerstick BG and ketone measurements will be repeated after 1 hour. The correction dose given may be adjusted by the subject during extended use of the system at home.
 
The subject will replace their infusion set infusion with a new infusion set and the correction bolus will be repeated as needed. Closed-loop will be disabled for the next 2-4 hours and until BG has returned to < 180 mg/dL. Subjects will report all positive ketone measurements to the investigators.
 
Study investigators will receive alerts for prolonged states of hyperglycemia.

Subject loses consciousness or has a seizure, or subject is unable to take
	
1 mg of glucagon will be administered and 911 will be called. The study will be stopped immediately until sponsor conducts a full investigation to determine the root cause for the compromised system performance and is able to
	
1 mg of glucagon will be administered by the subject's care partner/other responsible adult and 911 will be called. The study will be stopped immediately until sponsor conducts a full investigation to determine the root cause for the

oral carbohydrates	address all issues. Sponsor will also communicate the results of this root cause investigation to FDA and to study investigators.	compromised system performance and is able to address all issues. Sponsor will also communicate the results of this root cause investigation to FDA and to study investigators.

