No heart rate, no blood pressure	
Perform resuscitation, call 911, and transfer subject to ER.
 
Study will be stopped immediately until sponsor conducts a full investigation to determine the root cause for the compromised system performance and is able to address all issues. Sponsor will also communicate the results of this root cause investigation to FDA and to study investigators.
	
Perform resuscitation, call 911, and transfer subject to ER.
 
Study will be stopped immediately until sponsor conducts a full investigation to determine the root cause for the compromised system performance and is able to address all issues. Sponsor will also communicate the results of this root cause investigation to FDA and to study investigators.

Study staff will monitor the subject's sensor glucose and insulin delivery throughout the study using the iAPS on the subject's phone, the web interface and CGM. All blood glucose measurements will be performed with the study-approved glucometer.

Manual correction boluses may also be administered via the iAPS as needed throughout the hybrid closed loop phase.

For the extension phase (at home use) of the study device, study staff will follow the following detailed plan in response to notifications from the study system or contacts from subjects. Failure to document these actions in response to a notification or subject contact will be considered a protocol deviation.

Safety Monitoring Contact Plan for At Home Portion of Study

Plan	Team notifications	Plan
Hyperglycemia Mitigation plan	The study team will receive real time text alerts for CGM values: >180 mg/dL for >1.5 hours or >250 mg/dL for >20 minutes.	A study team member will contact participant to review fingerstick and ketone values, discuss etiology of hyperglycemia, and review with participant mitigation strategies including insulin coverage for hyperglycemia, ketone testing, set change, and/ or subcutaneous injection as indicated based on clinical scenario. A licensed

		
professional on the study team (MD or NP) will make these clinical decisions.
 
A study team member will recheck CGM remotely in 1 hour to ensure reduction in hyperglycemia.

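### Table 8 makes the recheck of a treated fingerstick low depend on CGM, so no recheck is clearly required at home; a lesser point is that its set-change test fails some corrections that reach target

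*Protocol*

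**What the plan says.** **Recheck after a low.** Section 3.2 of the Protocol defines hypoglycemia by a fingerstick below 63 mg/dL and/or symptoms, and requires carbohydrate for it. The HMS-alert row of Table 8 has two branches in each column, one for a confirmatory fingerstick of 63 or above and one for a fingerstick below 63. Treatment is optional in the first and required in the second. The follow-up sentence is the same in both: "Subjects will then perform a follow-up fingerstick measurement 15 minutes after treatment if CGM < 63 mg/dL". Both branches repeat until the HMS alert ceases. The next row, for a CGM reading below 63, instead continues until the fingerstick is above 63. Table 7 (section 6.6.1) calls for a fingerstick every 15 minutes from the time BG is below 63 until it is 63 or more.

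**Set change.** The row for BG confirmed above 180 for more than an hour with ketones below 1.0 mmol/L reads, in the home column: "Subject will deliver a manual correction bolus with a target of 140 mg/dL via the pump". Then: "Fingerstick BG and ketone measurements will be repeated after 1 hour". The failure test is "If BG fails to decrease by a minimum of 50 mg/dL in 1-2 hours, then subject will replace their infusion set". The supervised column applies the same test: "If BG fails to decrease by a minimum of 50 mg/dL in 1-2 hours, then study staff will replace the" set. Repeating the bolus is as needed at home and at the investigator's discretion in the session. The set change carries no such latitude in either column.

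**The concern.** A confirmed low receives the same follow-up as a reading that was not low, and the decision to look again is handed to the sensor. The protocol itself ranks the two sources the other way. It defines the event by fingerstick, section 6.6.4 tells participants that a fingerstick is generally the more accurate, and section 7.3.1.4 lists CGM over-reading as a hazard. Section 3.2 says that the HMS uses the same CGM data as the controller, so a silent alert does not confirm recovery independently. Section 2.2 notes that hypoglycemia in pregnancy raises the risk of unawareness, so absence of symptoms is weak reassurance. What is at stake is a treated low at home that has not resolved and that no clearly applicable rule requires anyone to recheck.

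In the set-change row, the dosing target and the test of success do not fit together just above the entry threshold. A participant whose correction did what it was dosed to do is told that her infusion set must be replaced.

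**Working it through.** **1. Recheck after a fingerstick below 63 at home.** Suppose the low has been treated and the fingerstick value is in fact still below 63 fifteen minutes later. Under the home column of Table 8:

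| CGM | HMS alert | Symptoms | What Table 8 requires |
|---|---|---|---|
| below 63 | either | either | Repeat fingerstick; the CGM-below-63 row applies and ends on the fingerstick |
| 63 or above | sounding | either | Confirmatory fingerstick, as for every predictive low alarm |
| 63 or above | silent | present | Fingerstick under the symptoms row |
| 63 or above | silent | absent | Nothing |

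Only the last line is a gap. Three other provisions bear on it:

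- The remote low alert in section 6.7 needs CGM below 54 for more than 20 minutes, so it cannot fire while CGM is 63 or above.
- Scheduled home fingersticks (before meals, 2 hours after meals, bedtime) may happen to catch the low, but section 6.3 allows them to be dropped after two weeks.
- Table 7's rule would close the gap if it applies at home. Its section heading refers to the closed-loop session, and its only row labelled as home use is CGM every 5 minutes.

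In the supervised session there is no gap in practice. Table 7 is stricter than Table 8, and following Table 7 satisfies both.

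To show the difference between the two rules, assume that the low lasts D minutes after treatment. D is an assumption; the documents give no figure. Rechecks under Table 7's rule are D/15: 1 for D = 15, 2 for D = 30 and 4 for D = 60. In the last line of the table, the HMS-alert row requires 0 in each case.

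**2. Set-change test.** Inputs from Table 8: entry at BG above 180, so 181 is the lowest whole-number start; bolus target 140; required fall 50.

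- Fall on reaching target = start - 140.
- From 181: 181 - 140 = 41, short by 50 - 41 = 9.
- From 189: 189 - 140 = 49, short by 1.
- From 190: 190 - 140 = 50, which passes.

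So nine whole-number starts, 181 to 189, fail when the bolus lands on its target. To pass, BG must end at start - 50, which is 131 from 181 and 139 from 189, below the target in every case. The fall needed exceeds the fall aimed for by 50/41 = 1.22 (22%) at 181, shrinking to 50/49 = 1.02 (2%) at 189.

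If the set change also requires BG to be above 140, reaching 140 triggers no set change from any start. From 190 upward nothing alters, because any BG of 140 or below is already a fall of at least 50.

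**The case against.** **On the recheck.** The case against a home gap has substance. The Schedule of Assessments marks protocol-required fingersticks in the Extension Phase column, and its footnote 2 ties them to hypo- and hyperglycemia criteria during closed-loop use, which home use is. Table 7 is titled for closed loop, and its 15-minute rule sits in a row labelled that way. Section 6.6.4 says that safety-plan fingersticks always remain in force, and that a fingerstick should replace CGM when its accuracy is in doubt. A reader might infer that the protocol plainly leaves women at home with no recheck after a confirmed low. The documents do not support that, because these provisions can be read to reach home use. They do not settle the matter either. The heading of section 6.6.1 limits it to the session, Table 8 has a specific home column with the CGM condition, the always-required safety plan is the plan that contains the condition, and the accuracy advice sits among the bolus-screen instructions.

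A reader might also take the 20%/20 mg/dL agreement criterion in section 6.3 as showing that an accepted sensor may read 63 or above beside a much lower fingerstick. That goes too far. The criterion is an aggregate one, met when at least 90% of values agree, and serves to decide whether scheduled fingersticks can stop. It is not a tolerance for a single reading.

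**On the set change.** The 140 mg/dL figure is a dosing aim and the 50 mg/dL fall is a screen for failed delivery; nothing says that they must coincide. A strict screen suits section 7.3.1.5, which notes that DKA in pregnancy can occur at lower glucose. Closed loop stays on in this row and may carry BG below 140, the dose may be adjusted, and once the at-home contact plan is activated an MD or NP decides on set changes. All of this stands. A reader might infer a miscalculation or a hazard to the participant. The documents show neither: the cost is an occasional unneeded set change, and the repeat bolus, the step that could cause a low, is discretionary.

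**Conclusion.** The main point holds and should be fixed. The HMS-alert row makes follow-up of a fingerstick-confirmed low depend on CGM, at odds with section 3.2, Table 7 and the next row of the same table. That inconsistency is firm on the text. The consequence at home is less certain: no recheck is clearly required when a low persists with CGM at 63 or above, the alert silent and no symptoms, and this rests on reading Table 7 as confined to the supervised session, which is the better reading but not the only one. How often that state would arise cannot be estimated from the documents, and the count of 4 rechecks against 0 is an illustration for an assumed one-hour low.

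The set-change point is minor. The mismatch is exact for starts of 181 to 189 and absent from 190 upward, and it errs towards caution. Neither point affects the primary endpoint definition or the sample size.

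**What to change.** **Main change.** In both columns of the HMS-alert row, after any fingerstick below 63 mg/dL, require a repeat fingerstick every 15 minutes until BG is at least 63, whatever CGM or the alert shows, and state that this applies during home use. The cost is a few extra fingersticks.

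**Minor change.** In both columns of the row for BG above 180 with ketones below 1.0, require the set change only if BG has fallen by less than 50 mg/dL and is still above 140. Keep the BG and ketone recheck at one hour so that screening for set failure continues. The cost is slightly fewer precautionary set changes.

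Both are wording changes to Table 8 and the matching training checklists, made through a protocol amendment, with no effect on design, sample size or visit schedule.

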6.6.5 General Usage Training and System Initiation

For extension phase continued use of the system, subjects will be instructed to use the system in closed-loop mode except 1) when no CGM sensor is available or 2) if insulin is delivered by any means other than the study pump (e.g. injection of subcutaneous insulin via syringe in the event

of infusion site failure). If insulin is delivered by any means other than the study pump, participant will be instructed to turn off closed-loop mode for approximately four hours.

The participant will also be instructed to contact study staff during periods of illness with an elevated temperature >101.5 degrees Fahrenheit (38.6 degrees Celsius), periods of significant illness, or during periods of use of medications such as epinephrine for the emergency treatment of a severe allergic reaction or asthma attack in addition to use of oral or injectable glucocorticoids to determine if closed-loop use should be temporarily discontinued.

Participants will be specifically instructed:

- 1) Not to upgrade the phone operating system.
- 2) Not to plug headphones into the study phone or alerts will be silenced.
- 3) Not to put the phone on vibrate mode or alerts will be silenced.
- 4) Not to use any manufacturer provided (e.g. Dexcom G6 Mobile App) or third-party components for CGM connectivity and monitoring, as this will interfere with connectivity to the study phone.

During the 48 hour training session, the subject's care partner must be trained on the following:

- Review device training including the alerts that are sent to the participant.
- Review study staff contact information.
- Mixing and giving glucagon, turning subject to the side, and call 9-1-1.
- Disconnecting the study pump.
- Review symptoms of hypoglycemia that can include sweating, jitteriness, and not feeling well, as well as the possibility of fainting or seizures (convulsions).
- Review symptoms of hyperglycemia to include increased thirst, urination, headaches, not feeling well, nausea, vomiting, and ultimately diabetic ketoacidosis.
- Review disconnecting the study devices.

Training of the care partner will be completed either in person or via video visit during a portion of the 48-hour study session, prior to discharging the subject home with the system for home use.

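### For home use, Table 8 and section 6.6.5 give different closed-loop off-periods after an injected correction for likely infusion set failure

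*Protocol*

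**What the plan says.** **Protocol section 7.2, Table 8**, row for BG confirmed above 180 mg/dL for more than 1 hour with ketones above 1.0 mmol/L:

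- Outpatient extension column: "a manual correction bolus with a target of 140 mg/dL is to be given via injection to assure proper absorption", the stated setting being likely infusion set failure. The participant changes the infusion set, and the correction may be repeated. Then: "Closed-loop will be disabled for the next 2-4 hours and until BG has returned to < 180 mg/dL".
- Inpatient column: the same window, with a named decision-maker: "Closed-loop will be disabled by the investigator for the next 2-4 hours and until BG has returned to < 180 mg/dL".

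**Protocol section 6.6.5** opens with its scope: "For extension phase continued use of the system, subjects will be instructed to use the system in closed-loop mode except" in two listed cases. One is the absence of a CGM sensor. The other begins "if insulin is delivered by any means other than the study pump (e.g. injection of subcutaneous insulin via syringe in the event", and the event it goes on to name is a failed infusion site. For that second case the "participant will be instructed to turn off closed-loop mode for approximately four hours". The section states no BG condition.

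Neither place cites the other, makes an exception for it, or says which prevails.

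**The concern.** The Table 8 outpatient row and section 6.6.5 describe the same situation: a participant at home whose infusion set has probably failed and who has taken insulin by injection. One gives a range starting at 2 hours plus a glucose condition. The other gives about four hours and no glucose condition.

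Three things depend on having one rule:

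- **Training.** Section 6.6.5 is the instruction given to participants before they go home, and Table 8 is the treatment plan they are to follow there. Staff cannot teach both as written.
- **Deviations.** Section 10.3 treats any noncompliance with the protocol as a deviation. A restart at 2.5 hours with BG 170 mg/dL complies with one section and departs from the other.
- **Event review.** Section 4.3 calls for a root cause analysis of events, and section 8.4 ties stopping to severe hypoglycemia or DKA related to system function. If such an event followed a restart, the protocol would give no single answer on whether the restart was as planned.

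**Working it through.** The plan states no figure to reproduce. The check sets the two rules side by side.

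**Inputs**

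| Element | Table 8, outpatient column | Section 6.6.5 |
|---|---|---|
| Phase | Home extension | Home extension |
| Trigger | BG > 180 mg/dL for more than 1 hour, ketones > 1.0 mmol/L, correction injected | Any insulin not given through the study pump; example is an injection for infusion site failure |
| Off-period | 2-4 hours | About 4 hours |
| BG condition | Off until BG < 180 mg/dL | None stated |
| Who picks the time within the range | Not named | Not applicable |

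**Step 1: do both rules reach the same event?** Yes. The Table 8 correction is injected, so it meets the trigger in section 6.6.5, and its reason is the one section 6.6.5 uses as its example. Both apply at home.

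**Step 2: what does each rule say at a given time?** Time is counted from a single injection. This is an assumption, because neither place says when its clock starts.

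| Time since injection | BG (mg/dL) | Table 8 | Section 6.6.5 | Agree? |
|---|---|---|---|---|
| 1.5 h | 170 | Off | Off | Yes |
| 2.5 h | 170 | Restart allowed | Off | **No** |
| 2.5 h | 200 | Off | Off | Yes |
| 4 h | 170 | Restart allowed | Restart allowed | Yes |
| 4.5 h | 200 | Off | Off-period over; silent on BG | **Only Table 8 keeps it off** |

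The times and BG values are illustrations chosen to fall on each side of the stated limits.

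**Step 3: size of the gap.** Earliest restart is 2 h under Table 8, if BG is already below 180 mg/dL, and about 4 h under section 6.6.5. The difference is about 4 − 2 = 2 h. If the upper end of the Table 8 range is used and BG is below 180 mg/dL, the difference is about 4 − 4 = 0 h. The gap is therefore between 0 and about 2 hours per event, depending on a choice within 2-4 hours for which the outpatient column gives no criterion. The word for approximately in section 6.6.5 gives some slack near four hours, but it does not reach down to two.

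**The case against.** **The two texts can be obeyed together.** A participant who stays off for about four hours and until BG is below 180 mg/dL complies with both. Section 6.6.5 can be read as a general instruction and the Table 8 row as a narrower one with an added condition. This is true and it limits the point: the clear clash is the part of the Table 8 range from 2 to just under about 4 hours. It does not remove the point, because no text tells anyone to combine the rules, and someone following Table 8 alone may restart sooner.

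**A clinician is likely to be involved.** At home, positive ketones are reported to the investigators. The contact plan in section 7.2 has staff call for CGM above 180 mg/dL for more than 1.5 hours, with an MD or NP making the decisions and a CGM recheck in 1 hour. Section 6.7 alerts staff after 2 hours out of closed loop. These steps reduce the practical risk, but none of them sets the off-period.

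**Stronger readings that the documents do not support:**

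- *That the rules clash equally in both directions.* Section 6.6.5 does make closed-loop use the default outside its two exceptions, so its default after four hours is to return. But it is silent on persisting hyperglycemia, while Table 8 addresses it directly. A repeat correction, if injected, could also start the section 6.6.5 period again. This direction is a gap more than a contradiction.
- *That the supervised session is affected.* Section 6.6.5 is confined to the extension phase. The inpatient column has the same 2-4 hours, but the investigator disables the system there.
- *That the rule decides which hours are analysed as closed-loop time.* Section 4.2 defines the primary endpoint as time in 63-140 mg/dL overall by CGM. Nothing in the protocol ties this off-period to the counting of hours.
- *That a given share of the injected dose is still active at 2 hours.* That would need an insulin action time and knowledge of how the controller treats injected insulin. Section 3.2 refers to an IDE appendix for insulin-on-board calculations, and that appendix is not among the documents.
- *That one of the two rules is the unsafe one.* The text shows only that they differ. Which is appropriate is a clinical matter.

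**Conclusion.** The point holds for home use. Two sections of the same protocol govern one safety event with different off-periods, and only one of them has a glucose condition. A restart from 2 to just under about 4 hours with BG below 180 mg/dL is allowed by Table 8 and barred by section 6.6.5. After about four hours with BG still at or above 180 mg/dL, only Table 8 says that closed loop stays off. The earliest restart differs by up to about 2 hours per event.

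The contradiction comes from the wording alone. The 2-hour figure assumes only that both periods run from the same injection. How often such events will occur cannot be judged from the protocol, and no effect on the endpoint analysis is claimed. This is a contained inconsistency in a safety instruction. It is worth correcting because participants apply it at home and because the correction is cheap.

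**What to change.** Reconcile the outpatient column of the Table 8 row for ketones above 1.0 mmol/L with section 6.6.5:

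1. State one off-period for insulin given outside the study pump at home, and say when it starts, including after a repeat injection.
2. State one position on BG: whether a BG condition applies to restarting, and if so which.
3. Have each section refer to the other, and carry the same wording into the training checklist.

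The sponsor's clinicians decide the period and the BG position. Aligning the inpatient column is optional. That column also contains a sentence on stopping closed-loop use at home without a duration, which could be moved or cross-referenced in the same edit.

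The cost is a sentence or two of protocol clarification and a checklist edit. Sample size, endpoints and data collection do not change.
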